7.10 Safety Evaluation

All summaries of Adverse Events will be primarily reported, but not limited to, for the ITT population.

The Clinical Events Committee (CEC) will be responsible for the review and adjudication of all adverse events per the definitions established in the CEC Charter/Manual of Operations.

Site Reported and CEC adjudicated events shall be summarized in incidence and frequency tables coded by System Organ Class (SOC) and MeDRA preferred term (PT).

A table reporting CEC adjudication disposition will be presented (Site Reported, CEC adjudicated).

CEC adjudicated Adverse Events will be mapped to preferred terms and body systems using the Medical Dictionary for Regulatory Activities (MedDRA) coding dictionary. The number and percentage of subjects experiencing Adverse Events will be summarized by system organ class and preferred term for all Adverse Events.

CEC adjudicated Adverse Events will be presented by system organ class and preferred term.

Summaries of CEC adjudicated AEs by the maximal severity (Mild, Moderate and Severe), relatedness (e.g., to the study device, procedure, anti-platelet therapy.), seriousness (serious, non-serious) and timing (Peri-procedural- Day 0, Acute- day 1-30 and Delayed, Day 31-Study Exit) shall be presented.

Causality Assessment (Relatedness)

CEC adjudicated relationship of each adverse event will be presented as follows:

- Device: Medical device: (Medical device investigated in the Investigation)
- Procedure: The medical -surgical procedure on day 0
- Anti-platelet therapy: Related to the anti-platelet agent therapy, that is required per standard of care for treatment.

Missing and Partial Adverse Event Dates

The recorded dates for adverse events are important for an accurate tabulation of both events and patients, and required for the following:

1. Defining the start of the event
2. Designation of unique adverse event occurrences recorded intra-patient.

Completely missing or partially missing adverse event dates will be imputed as follows:

- If the adverse event start date is completely missing the adverse event will be counted to the date of the study procedure.
- If the adverse event start date is partially missing and the partial date is not sufficient to determine if the event occurred after the start of the study procedure, then the adverse event will be counted with a start date of the procedure date.

Summaries of Adverse Events

All summaries of adverse events will be reported for the ITT and ICA population and based on counted adverse events.

Site Reported events shall be summarized. Adverse events will be mapped to preferred terms (PT) and system organ class (SOC) using the Medical Dictionary for Regulatory Activities (MedDRA) coding dictionary.

The number and percentage of patients experiencing adverse events will be summarized by system organ class (SOC), MeDRA preferred term and

In addition to a similar table, CEC adjudicated data will additionally be presented by:

Relatedness: Summaries AE relatedness (e.g., to the Pipeline™ device with Shield Technology™, procedure, and anti-platelet therapy.) by SOC and MeDRA.

Seriousness: Serious and non-serious adverse events will be presented by SOC and MeDRA PT.

Severity: With respect to maximal severity, will be presented by SOC and MeDRA PT

Timing: With respect to timing, will be presented by Peri-Procedural (Day 0), Acute (Day 1-30) and Delayed (Day 31-study exit) per SOC and MeDRA PT

The number and percentage of patients experiencing 1 or more adverse events will be presented counts of events and percentages.

A table entitled *Summary of CEC Adjudicated Adverse Events by System Organ Class and Preferred Term by Site* contains the primary presentation of the adverse event data by site. This table is prepared without defining the causality or relationship to the study procedure or device. Patients will be counted only once at the system organ class level and will be counted once for each applicable preferred term; multiple occurrences of the same preferred term for a patient will only be counted once, in addition the event counts will be provided for completeness of data. The number and percentage of patients experiencing each event by system organ class and preferred term will be displayed. System organ classes, and preferred terms within a system organ class will be displayed alphabetically. The overall adverse event rates will be summarized using counts and percentages. This table will be repeated for the site-reported adverse events; results will be summarized and presented in a table entitled *Summary of Site Reported Adverse Events by System Organ Class and Preferred Term by Site*.

A table entitled *Summary of CEC Adjudicated Adverse Events by Preferred Term Leading to Study Discontinuation* provides the presentation of adverse events leading to study discontinuation. This table

will have the same structure as that of the previously described table however, only those adverse events that led to study discontinuation will be displayed. The number and percentage of patients experiencing each system organ class and preferred term will be displayed.

A listing entitled *Adverse Events (Site Reported)* provides supportive data and is sorted by patient and relative day of the study procedure.

A listing entitled *Adverse Events (CEC Adjudicated)* provides supportive data and is sorted by patient and relative day of the study procedure.

A patient profile shall be generated for each individual patient detailing all adverse events mapped to their adjudicability status and CEC adjudicated disposition. The heading for each profile will contain the patient identifier; the collective set of all profiles will be titled *Profile of Adverse Events by Patient*. A listing presenting this information will be included in a listing entitled Adverse Event Mapping. A summary table presenting the number of site reported events deemed adjudicable and their adjudication disposition will be presented in A table entitled *Summary of Site Reported Adverse Events and Adjudication Status*.

7.11 Health Outcomes Analyses

This section is not applicable to this study.

7.12 Changes to Planned Analysis

Planned analyses will be performed as indicated and per CIP. Other analyses can be conducted addition to the prespecified analyses as to further elucidate findings that may be useful to the Sponsor or the medical community.

7.13 Analyses in addition to the CIP (to include but not limited to:)

7.13.1 Additional Analyses

Within the study protocol there was no declaration regarding the ranking of the analyses. Additionally, there was no formal statistical testing strategy or formal estimate regarding the sample size and statistical power for this clinical investigation. For presentation of the results, the analyses will be categorized into 2 major categories: ***Device and Peri-Procedure Analyses*** and ***Post-Procedure Analyses***.

7.13.2 Device and Peri-Procedure Analyses

The **Device and Peri-Procedure** analyses to be summarized will address device deployment. Within this analysis, there are 9 separate variables:

- Successful deployment of the study device to the target site. Successful deployment has a binary outcome and comes directly from the clinical case report form.
- Implantation of the study device. The determination of implantation has a binary outcome and comes directly from the clinical case report form.
- Number of times re-sheathing was performed. The count (0, 1, 2, or >2) comes directly from the clinical case report form.
- Entire IA neck covered by the study device. Complete neck coverage has a binary outcome and comes directly from the core lab.

- Achievement of wall apposition; a binary endpoint that comes directly from the core lab
- Device deficiency/ malfunctions; a binary endpoint and comes directly from the clinical case report form.
- Procedure time, a continuous variable and comes directly from the clinical case report form
- Cumulative Fluoroscopy time, a continuous variable and comes directly from the clinical case report form
- Serious Adverse Events during the procedure (Day 0)

7.13.3 Post-Procedure Analyses

The first series of **Post-Procedure** analyses to be summarized will address the outcomes after the procedure. Within this series, there are 9 separate parameters:

- Aneurysm occlusion (Class 1: Complete obliteration, Class 2: Residual neck, or Class 3: Residual Aneurysm), derived from the post-procedure imaging adjudicated by Core Lab.
- Modified Rankin Scale (mRS); a multinomial endpoint that comes directly from the site reported case report form for evaluating the intra-patient over time and the change from baseline. The mRS will be scored for each patient by an evaluator at the clinical site. The mRS is a well-accepted and defined scoring system for measuring the degree of disability or dependence in the daily activities of people who have suffered a stroke using a multinomial ordinal scale:
 - 0 No symptoms at all
 - 1 No significant disability despite symptoms; able to carry out all usual duties and activities
 - 2 Slight disability; unable to carry out all previous activities, but able to look after own affairs without assistance

The mRS score at 1 year will be dichotomized (>2 vs. ≤ 2) and summarized using counts, percentages, and 2-sided 95% exact binomial confidence intervals.

- NIH Stroke Scale (NIHSS); a continuous endpoint that comes directly from the site reported clinical case report form for evaluating the intra-patient over time and the change from baseline. The NIHSS is a 15-item neurologic examination stroke scale used to evaluate the effect of acute cerebral infarction on the levels of consciousness, language, neglect, visual-field loss, extraocular movement, motor strength, ataxia, dysarthria, and sensory loss.
- Platelet reactivity testing, based on the VerifyNow, VASP, MEA, TEG, LTA testing reported as a percentage. A continuous endpoint that comes directly from the site reported clinical case report form.
- Change in antiplatelet therapy because of the platelet reactivity testing; a binary variable and comes directly from the site reported clinical case report form.
- Retreatment of the target aneurysm; a binary variable adjudicated by the imaging core laboratory. The recurrence of the aneurysm will be summarized using the percentage of subjects that experience aneurysm recurrence. Aneurysm recurrence is defined as an aneurysm that achieves complete occlusion at 6 months post-procedure, and then is no

longer completely occluded, based on Core Lab, (i.e., residual neck or residual aneurysm is found by Core Lab) at 12 months post-procedure. This endpoint will only be defined in those subjects with both 6- and 12-month imaging adjudicated. The percentage of subjects that undergo retreatment of the target aneurysm after the initial PED treatment will also be presented. Major stroke in the territory supplied by the treated artery or neurological death at 30 days post-procedure due to procedural complications; the event and event-relatedness will be adjudicated by the CEC. The 1-year event rate will also be tabulated and reported. A binary variable, and the event will be adjudicated by the CEC.

- Intracerebral hemorrhage (ICH) > 30 days post-procedure; the event will be adjudicated by the CEC. The 1-year event rate will also be tabulated and reported. A binary variable, and the event will be adjudicated by the CEC.
- Parent artery stenosis; continuous variable from the post-procedure imaging adjudicated by Core Lab, dichotomized into >50% and ≤50% stenosis. Additionally, stenosis will be presented by quartile.
- Device migration; a categorical variable from the post-procedure imaging adjudicated by Core Lab.

The second series of **Post-Procedure** variables to be summarized will address the safety and efficacy profile over the course of the entire clinical investigation.

- The device-related neurologic adverse event rate at 1 year post-procedure will be presented with the relationship between the device and the neurologic adverse events adjudicated by the independent CEC. Disabling stroke or neurological death at 1 year (as observed)
- Ischemic and Hemorrhagic Cerebrovascular Events (as adjudicated by CEC) : includes incidence of Stroke (Major or Minor, Ipsilateral or Contralateral), Cerebral Infarction (Symptomatic or Asymptomatic), Intracranial Hemorrhage, Transient Ischemic Attack, and Target Aneurysm Rupture
- Aneurysm recurrence
- Device Related Serious Adverse Events
- Procedure related Serious Adverse Events

8. Validation Requirements

Output will be validated by level I or II validation.

Level I: The peer reviewer independently programs output and then compares the output with that generated by the original Statistical Programmer.

Level II: The peer reviewer reviews the code; where appropriate, performs manual calculations or simple programming checks to verify the output.

9. References

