1.3 Rationale of the Clinical Study

The Pipeline™ Embolization Device demonstrates high efficacy and a good safety profile in treating aneurysms of diverse morphology. Continued development of the PED delivery system resulted in the Pipeline™ Flex Embolization Device (PFED), which incorporates a resheathing mechanism, allowing the physicians to reposition and redeploy the PED braid. Additionally, polytetrafluoroethylene (PTFE) sleeves are used in place of the protective coil, resulting in the elimination of the need to torque the delivery system to release the PED braid. The latest developmental modification to the PED system is Shield Technology™. Shield Technology™ utilizes a phosphorylcholine (PC) surface treatment to the existing implant combined with the PFED delivery system. The Shield Technology™ surface treatment applied to the implant is an inert, PC polymer material that is chemically bonded to the braid surface. The polymer is a chemically derived material, created to mimic the outer membrane of a human red blood cell. Shield Technology™ reduces the material thrombogenicity of the braid surface compared to the current bare metal PFED implant based on bench data with human platelets and plasma. The study described herein will evaluate the performance of the Pipeline™ Flex Embolization Device with Shield Technology™ in a broad real-world clinical setting.

Platelet inhibition with dual antiplatelet therapy (DAPT); consisting of aspirin and a thienopyridine, is necessary for the prevention of acute or subacute thrombosis and related complications after neurointerventional procedures.⁴² DAPT has been associated with a reduction in thromboembolic events, but has also been implicated as a potential factor contributing to the rates of ischemic and hemorrhagic complications associated with PED placement.⁴² Current DAPT protocols used in PED patients are developed based on studies in the field of cardiology and interventional radiology. In addition, there is no consensus on the optimal DAPT regimen, dose, and duration.⁴³ This study aims to collect data on platelet function testing, DAPT regimens, optimal dose, and post-PED DAPT duration to identify their association with thrombotic and hemorrhagic adverse events in the clinical setting and evaluate related clinical outcomes.

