The patient will be tested at the discretion of the site per standard of care procedures for antiplatelet response and the appropriate dose of antiplatelet agents will be given after the Pipeline™ device with Shield Technology™ placement procedure. Medications could be continued as medically indicated.

Estimated Duration of Patient Participation

Up to 200 subjects will be enrolled over a period of approximately 24 months. The study is intended to have 200 subjects undergo attempted deployment of the Pipeline™ device with Shield Technology™. Each study patient will be followed for 1 year after the primary study procedure. Study participation includes consent, initial screening and baseline, treatment using the Pipeline™ device with Shield Technology™, discharge exam and follow-up visits at approximately 30, 90, 180 days, and 1 year. The total study duration is expected to be approximately 3 years.

Schedule of Assessments

	Baseline	Procedure	Discharge	1 Month	3 Months	6 Months	1 Year	Unscheduled
Schedule		Day 0		±14 days	±30 days	±6 weeks	±8 weeks	
Eligibility	X							
Demographics	X							
Aneurysm Symptoms	X	O	O	O	O	O	O	OR
Medical History		X						
Study Procedure		X						
Procedure Imaging		XR						
Ancillary Devices		X						
Study Device		XR						
Discharge			X					
Follow Up				X	X	X	X	XR
Follow-Up Imaging				OR	OR	OR	OR	OR
NIHSS	O	X		O	O	O	O	OR
mRS	O	X		O	O	O	O	OR
Exit			X					

Retreatment Study Procedure				OR	OR	OR	OR	OR
Labs	OR	OR	O	O	O	O	O	OR
Device Specific Event		OR	OR	OR	OR	OR	OR	OR
Adverse Event Assessment		OR	OR	OR	OR	OR	OR	OR

Key: Required=X Optional=O Repeatable=R

ANALYSIS POPULATIONS

The following populations will be considered for the analysis of data for this study:

Intent to Treat (ITT)

The Intention to Treat (ITT) population includes all consented subjects in whom deployment of the Pipeline™ device with Shield Technology™ was attempted.

Full Analysis Set (FAS)

The Full Analysis Set (FAS) population is a subset of the ITT population including only those subjects in whom the Pipeline™ device with Shield Technology™ was implanted.

Internal Carotid Artery (ICA) Population

The Intra-Cranial Artery Population (ICA) is a subset of the ITT population including only those subjects in whom the Pipeline™ device with Shield Technology™ was implanted in the ICA (segments C2-C7).

Non-ICA Population

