7.2.2 General Conventions for Summarization

Summary statistics will consist of the number and percentage of responses or counts at each level for categorical variables (e.g. gender). For continuous variables, the sample size (n), mean, median, standard deviation (SD), minimum, and maximum values will be presented.

All mean and median values will be formatted to one more decimal place than the measured value. Standard deviation values will be formatted to two more decimal places than the measured value. Minimum and maximum values will be presented with the same number of decimal places as the measured value.

The number and percentage of responses will be presented in the form XX (XX.X%).

- All summary tables will include the analysis population sample size (i.e., number of subjects).
- Relative Study Day 0 is defined as the day the patient underwent the study procedure. All study days are determined relative to the day the patient underwent the study procedure.
- Baseline values will be defined as those values recorded immediately prior to the study procedure.
- Change from baseline for differences will be calculated as follows:

$$\text{Change} = \text{Post-baseline value} - \text{baseline value}$$

- Missing data may have an impact upon the interpretation of the trial data. The primary presentation of the overall primary endpoint results will be based on the observed data with multiple imputation for missing data using SAS PROC MI. A methodology is also defined in this section for addressing missing dates.
- Date variables will be formatted as DDMMYYYY for presentation; SAS Date9. format.

Data from this study, when applicable will be presented in a listing format. All listings will be sorted by patient number and date, as applicable.

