Subjects may undergo (as indicated by site per standard of care) a neurologic examination and assessment using the mRS and NIHSS at baseline and also prior to the procedure. Data will be summarized and reported in a table entitled Summary of Neurological Assessments at Baseline (ITT population); a similar table will be restricted to the ICA population. The summary will include the baseline results for the mRS (Baseline) and NIHSS (recorded pre-procedure). The mRS, results will be presented using counts and percentages for each mRS score. For the NIHSS, results will be summarized using descriptive statistics as observed.

A NIHSS table will be presented in a listing format entitled NIH Stroke Scale (NIHSS) Scores will contain the baseline pre-procedure and post-procedure scores by patient, as well as the date and time the score was recorded. This listing will be sorted by patient number. As the screening/baseline assessments may be performed prior to the procedure at Day 0 some subjects will have only a single value for NIHSS. In this case the screening/baseline value will be left blank in the listing. A listing entitled Modified Rankin Scale (mRS) Scores will contain the pre-procedure and post-procedure scores by patient and date the score was recorded. This listing will be sorted by patient number.

Platelet Reactivity Test Results

Data will be summarized and reported in a table entitled Summary of the Platelet Reactivity Test Results Recorded at Baseline (ITT population); a similar table will be restricted to the ICA population. The last results prior to the procedure will be reported for each patient. The platelet test results will be summarized using descriptive statistics: n, arithmetic mean, standard deviation, median, range (i.e., minimum and maximum values). Subjects with missing data that cannot be resolved prior to database lock will not be included in the tabulation and excluded from the summary statistics; all data will be presented in a listing. A summary of the platelet reactivity data recorded after the procedure will be presented in a table entitled Summary of Post-Procedure Platelet Reactivity Test Data; a similar table will be restricted to the ICA population. The supportive data for Table platelet reactivity will be presented in a listing format entitled Platelet Reactivity Test Results. This listing will be sorted by patient number. The individual elements to be presented from the CRF are presented below.

[Redacted content]

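### SAP 7.13.3 treats five platelet assays as one continuous percentage, and the visible summary rules give no split by assay, unit or agent tested

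*SAP*

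**What the plan says.** SAP 7.13.3 lists platelet reactivity testing as one post-procedure parameter, "based on the VerifyNow, VASP, MEA, TEG, LTA testing reported as a percentage". It then classes the item as a continuous endpoint taken from the site-reported case report form. This is the only visible definition of the variable.

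For baseline, SAP 7.6 (Platelet Reactivity Test Results) says "The last results prior to the procedure will be reported for each patient", and "The platelet test results will be summarized using descriptive statistics: n, arithmetic mean, standard deviation, median, range". For later results, the same section says "A summary of the platelet reactivity data recorded after the procedure will be presented in a table" and names no statistics there, so the general rule in SAP 7.2.2 applies: "For continuous variables, the sample size (n), mean, median, standard deviation (SD), minimum, and maximum values will be presented".

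SAP 7.7 again carries platelet reactivity as one of ten parameters to be summarised at five time points, with no breakdown.

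On how the tests come about, SAP section 5 (Study Procedure) says "The patient will be tested at the discretion of the site per standard of care procedures for antiplatelet response". Protocol 1.3 describes therapy as dual, and gives the purpose of collecting platelet function and regimen data as "to identify their association with thrombotic and hemorrhagic adverse events". Protocol 3.1 and 9.4 both list platelet reactivity results among the data to be analysed.

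**The concern.** A mean, SD, median or range describes something only if the values share a scale and measure the same thing. Here the values may come from any of five tests and may reflect the response to either of two agents. The SAP gives no conversion between tests and no statement that their percentages are interchangeable. It also has no rule for a patient tested by more than one method, or for more than one agent.

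Two consequences follow. The summary depends on the mix of assays at the sites that contribute data, so it describes local practice as well as the patients. And if assay follows site, any relation between the unsplit value and thrombotic or hemorrhagic events is entangled with other differences between sites. That second consequence touches a purpose the protocol states for these data.

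**Working it through.** The plan gives no mean, SD, sample size or expected value for platelet reactivity, so there is no figure to reproduce. The check is first one of text, then an illustration.

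**Text, side by side**

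- Definition (SAP 7.13.3): five assays, one scale, one continuous variable.
- Baseline summary (SAP 7.6): last pre-procedure results; n, mean, SD, median, range. No stratum by assay or agent.
- Post-procedure summary (SAP 7.6 with 7.2.2): one table; n, mean, median, SD, minimum, maximum. No stratum.
- Summary over time (SAP 7.7): one parameter at five time points. No stratum.
- Source of variation: testing at site discretion, up to 25 sites (Protocol 4.2), two agents (Protocol 1.3). The SAP schedule of assessments marks labs as optional at every time point where they appear. If platelet tests fall under that row, the patients and sites contributing values can also change from visit to visit.

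Followed literally, these rules produce summaries that mix assays and agents.

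**Illustration (every input is an assumption; none comes from the documents)**

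Take five assays in equal shares, a within-assay SD of 15 points, and assay means evenly spaced by *d* points around 50.

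- Between-assay variance = d² × (4 + 1 + 0 + 1 + 4)/5 = 2d².
- Pooled SD = √(15² + 2d²).
- Between-assay share of variance = 2d²/(225 + 2d²).
- Now let the mix move from 20/20/20/20/20% to 10/10/20/30/30% between two visits, with nothing changing within any assay. The pooled mean moves by d × (−0.2 − 0.1 + 0 + 0.3 + 0.6) = 0.6d.

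| Spacing d | Pooled SD | Between-assay share | Shift in pooled mean |
|---|---|---|---|
| 0 | 15.0 | 0% | 0 |
| 5 | √275 = 16.6 | 50/275 = 18% | 3 |
| 10 | √425 = 20.6 | 200/425 = 47% | 6 |
| 20 | √1025 = 32.0 | 800/1025 = 78% | 12 |

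A simpler case with two equally used assays 20 points apart and the same within-assay SD gives √(15² + 10²) = 18.0.

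The first row is the case in which pooling does no harm: one scale and one common mean. The SAP neither states nor justifies that this case applies.

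**The case against.** The strongest reply is that nothing in the SAP says in words that the five assays will be pooled. SAP 7.13.3 names the tests and the variable type. SAP 7.6 says the results will be summarised, which is compatible with one row per test. Redacted text follows directly, and the purpose of all of it cannot be seen. This stands as far as it goes: a reader might infer that the plan prescribes one pooled mean and SD, but that is the natural reading, not an explicit instruction. Median and range are planned as well, although mixing affects them too. The redacted block that closes the platelet text in SAP 7.6 is introduced as listing content. A listing that shows the assay would not change the definition of the summarised variable.

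Other stronger readings also fail:

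- **A planned change from baseline would be corrupted.** SAP 7.13.3 specifies change from baseline for mRS and NIHSS but not for platelet reactivity. SAP 7.2.2 gives only a generic formula. The risk arises when a reader compares the separate baseline and post-procedure tables.
- **The Protocol 1.3 aim cannot be met.** That aim also covers regimens, dose and duration. Patient-level results will be listed, therapy change prompted by testing is a separate binary variable, and no visible text plans an association using an unsplit value. The supported statement is narrower: the summary cannot be interpreted for that aim without assay and agent.
- **The assays are shown not to be interchangeable.** The documents give no units or ranges by assay, so this cannot be shown from them. They equally contain nothing that supports a common scale, and it is the plan that adopts one.
- **Assay type is already recorded.** Naming five tests makes this plausible, but the CRF elements are redacted.

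It is also fair to say that site discretion over testing implies, and does not state, that assays differ between sites.

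**Conclusion.** The point holds in limited form. The SAP defines one continuous percentage from five assays, and its visible summary rules have no split by assay, unit or agent tested. Read as written, the tables mix assays and agents and depend on which sites use which test.

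The size of the distortion in this study is unknown. The illustrated shifts of 0 to 12 points and pooled SDs of 15.0 to 32.0 rest wholly on assumed means, SD and assay shares. They show only that the effect can range from nil to dominant. The conclusion also assumes that more than one assay is in use and that no redacted text sets a split.

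The stakes are low. Platelet reactivity is neither a primary nor a secondary endpoint in the SAP, and Protocol 9.2 sets no success criterion and makes all analyses descriptive. It is still more than missing detail, because a clearly better summary than the single percentage is available at little cost and serves a purpose the protocol states.

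**What to change.** In SAP 7.13.3, replace the single percentage with one variable per assay and agent tested, in that assay's own unit. In SAP 7.6 and 7.7, present n, mean, SD, median and range by assay and agent, with the number of patients tested by each assay at each time point. State that any before/after comparison, and any association with thrombotic or hemorrhagic events, uses results from the same assay only. Add a rule for patients with more than one assay or agent result before the procedure.

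The cost is a few more table rows and a smaller n in each. With at most 200 subjects, all tested and spread evenly over five assays (an assumption), a row would hold about 200/5 = 40. No new procedure is needed, provided the CRF captures both assay and agent. The sponsor should confirm that, because those fields are redacted.
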